VERTEX PHARMACEUTICALS INCORPORATED

PASS / Study 101 Information

Title	Long-term registry-based study of patients with transfusion-dependent	
	β -thalassemia (TDT) or sickle cell disease (SCD) treated with	
	exagamglogene autotemcel (exa-cel)	
Protocol version identifier	VX22-290-101, Version 2.1	
Date of last revision of protocol	15 November 2024	
HMA-EMA Catalogue number	This study will be registered in the HMA-EMA Catalogue of RWD Studies following PRAC approval of the final protocol, and before study initiation.	
Active Substance	exagamglogene autotemcel (exa-cel)	
Medicinal Product	Casgevy®	
Product Reference	EMEA/H/C/005763	
Procedure Number	N/A	
Marketing authorization holder(s)	Vertex Pharmaceuticals (Ireland) Limited	
Joint PASS	No	
Research Question and Objectives	Primary	
	1. Evaluate long-term safety outcomes in patients who received exa-cel for treatment of TDT or SCD	
	2. Evaluate long-term safety outcomes in patients who received exa-cel for treatment of TDT or SCD in comparison to patients receiving allo-HSCT	
	Secondary	
	1. Evaluate long-term effectiveness outcomes in patients who received exa-cel for treatment of TDT or SCD	
	2. Evaluate long-term effectiveness outcomes in patients who received exa-cel for treatment of TDT or SCD in comparison to patients receiving allo-HSCT	
Country(-ies) of Study	Germany, France, Italy, UK, US	
Author	Vertex Pharmaceuticals Incorporated	
	[name]	
	[name]	

Marketing Authorization Holder(s)

Marketing Authorization Holder(s)	Vertex Pharmaceuticals (Ireland) Limited
Authorized contact person for communication between the MAH and the EMA	Vertex Pharmaceuticals (Europe) Limited [name]

CONFIDENTIAL

This document contains confidential information. Any use, distribution, or disclosure without the prior written consent of Vertex Pharmaceuticals Incorporated is strictly prohibited except to the extent required under applicable laws or regulations. Persons to whom the information is disclosed must be informed that the information is confidential and may not be further disclosed by them.

allo-HSCT	allogeneic HSCT		
ANC	absolute neutrophil count		
Cas9	CRISPR-associated protein 9		
CBC	complete blood count		
CI	confidence interval		
CIBMTR	Center for International Blood and Marrow Transplant Research		
CIC	cardiac iron concentration		
CDM	Common Data Model		
CPI	continuous process improvement		
CRF	comprehensive research form (form type from CIBMTR)		
CRISPR-Cas9	clustered regularly interspaced short palindromic repeats and CRISPR-associated 9 nuclease		
EBMT	European Society for Blood and Marrow Transplantation		
eGFR	estimated glomerular filtration rate		
exa-cel	exagamglogene autotemcel (Casgevy), formerly known as CTX001		
FU	follow-up		
GDPR	General Data Protection Regulation		
gRNA	guide RNA		
Hb	hemoglobin		
HbA	adult Hb		
HBB	gene encoding the Hb beta subunit		
HbF	fetal Hb		
HbS	sickle cell Hb		
НСР	healthcare provider		
HIPAA	Health Insurance Portability and Accountability Act		
HLA	human leukocyte antigen		
HMA-EMA Catalogue	Heads of Medicines Agencies and European Medicines Agency joint catalogue (former EU PAS Register)		
HSCT	hematopoietic stem cell transplantation		
IA	interim analysis		
ICH	International Council for Harmonization		
IRB	institutional review board		
LIC	liver iron concentration		
MAH	Marketing Authorization Holder		
MRI	magnetic resonance imaging		
NI	non-interventional		
NMDP	National Marrow Donor Program		
OMOP	Observational Medical Outcomes Partnership		
RBC	red blood cell		
RNA	ribonucleic acid		
RWD	real world data		
SAE	serious AE		
SCD	sickle cell disease		
TDT	transfusion-dependent β-thalassemia		

Abbreviation	Definition	
TED	transplant essential data (form type from CIBMTR)	
TNM	tumor, lymph node, metastasis classification system	
UK	United Kingdom	
US	United States	
USA	United States of America	
VOC	vaso-occlusive crisis	

3 **RESPONSIBLE PARTIES**

Vertex Investigator(s)	Vertex Pharmaceuticals, USA
Registry Investigator(s)	EBMT, Netherlands
	CIBMTR, USA

ABSTRACT

4

Title	Long-term registry-based study of patients with transfusion-dependent β -thalassemi (TDT) or sickle cell disease (SCD) treated with exagamglogene autotemcel (exa-cel		
Rationale and Background	β -thalassemia is an inherited autosomal recessive blood disease characterized by reduced hemoglobin (Hb) production. Caused by mutations in the HBB gene, disease severity varies across a spectrum from intermedia to thalassemia major. β -thalassemia major, also called TDT, is fatal within the first few years after diagnosis if left untreated. Symptoms of TDT appear within the first 2 years of life and include severe anemia, splenomegaly, bone marrow expansion, failure to thrive and ultimately, death.		
	SCD is caused by a single nucleotide substitution in which a valine replaces a glutamic acid at position 6 of the β -globin chain leading to an abnormal or sickle Hb (HbS). HbS polymerizes in the deoxygenated state producing abnormal, sickle shaped red blood cells (RBCs) with limited flexibility and lifespan. These rigid cells are responsible for painful vaso-occlusive crisis (VOC), chronic anemia, inflammation, stroke, organ failure, and early mortality.		
	Exa-cel is a gene-edited cellular advanced therapy medicinal product administered through autologous hematopoietic stem cell transplantation (HSCT) to treat disorders caused by genetic defects that affect the production or function of Hb molecules, specifically β -thalassemia and SCD.		
	Information regarding long-term safety and effectiveness of therapy under the real-world conditions of use will be informative to patients, caregivers, and prescribers. Existing HSCT registries provide a mechanism to obtain these data.		
Research Question	Primary		
and Objectives	1. Evaluate long-term safety outcomes in patients who received exa-cel for treatment of TDT or SCD		
	2. Evaluate long-term safety outcomes in patients who received exa-cel for treatment of TDT or SCD in comparison to patients receiving allogeneic HSCT (allo-HSCT)		
	Secondary		
	1. Evaluate long-term effectiveness outcomes in patients who received exa-cel for treatment of TDT or SCD		
	2. Evaluate long-term effectiveness outcomes in patients who received exa-cel for treatment of TDT or SCD in comparison to patients receiving allo-HSCT		
Study Design	This will be a long-term, prospective observational cohort study using primary and secondary data collected by established international HSCT registries: the European Society for Blood and Marrow Transplantation (EBMT) Registry and the Center for International Blood and Marrow Transplant Research (CIBMTR) Registry.		
	The study will follow patients who received exa-cel for treatment of TDT or SCD following approval of the therapy in Germany, France, Italy, and UK (via EBMT) and US (via CIBMTR). In addition, comparator populations of patients with TDT or SCD receiving an allo-HSCT from the same countries and same transplant centers		

Data on a broad range of safety and effectiveness outcomes, as well as important covariates, will be collected within EBMT and CIBMTR via existing standard registry forms and custom, study-specific reporting forms.

The study enrolment period will continue for approximately 3 years following approval of exa-cel (in the respective region) and may be extended to up to 5 years enrollment. Eligible patients with TDT or SCD who are treated with exa-cel or receiving an allo-HSCT from the participating transplant centers and who consent to study participation will be included. Included patients will be followed for up to 15 years after the administration of exa-cel or allo-HSCT.

Measures to ensure long-term follow-up will include a combination of both transplant center and patient-specific interventions and will be applied to both exa-cel and allo-HSCT recipients.

In addition, participating EBMT and CIBMTR transplant centers will be trained to report directly to the Marketing Authorization Holder (MAH) information on all serious adverse events (SAEs), regardless of causality, among exa-cel recipients.

Should a hematologic malignancy be diagnosed in any patient receiving exa-cel in this study, participating centers will be instructed to contact the MAH to report the event and determine appropriate samples for analysis. The MAH will follow appropriate testing strategies to assess whether the malignancy developed as a result of off-target editing.

Population All patients with TDT or SCD, treated at participating centers reporting data to EBMT or CIBMTR, and receiving exa-cel or allo-HSCT from the date of approval of exa-cel through the end of the enrolment period will be the source population for this long-term follow-up study.

All patients treated with exa-cel during the enrollment period will be eligible to enroll. Patients receiving allo-HSCT will only be eligible for comparator cohort inclusion if, at the time of enrolment, they are of an age approved for exa-cel.

Eligibility will further require patient's informed consent / assent to allow data collection for the purposes of this study.

To address the study objectives, the following longitudinal cohorts will be established within each registry:

- 1. Patients who received exa-cel for treatment of TDT (TDT Exa-cel Cohort)
- 2. Patients who received exa-cel for treatment of SCD (SCD Exa-cel Cohort)
- 3. Patients who received allo-HSCT for treatment of TDT (TDT Allo-HSCT Cohort)
- 4. Patients who received allo- HSCT for treatment of SCD (SCD Allo-HSCT Cohort)
- Variables Primary disease diagnosis and exposure variables will be collected at the time of patient enrolment. Safety and effectiveness outcomes will be collected during the post-transplant period; pre-transplant data corresponding to the key outcomes of interest will also be collected to allow assessment of disease status over time. Additional key variables will be collected at the time of patient enrolment and/or during the post-transplant period, as appropriate. All variables will be collected for each patient cohort, unless otherwise noted.

	Category	Overview of Variables
	Primary Disease	• β-thalassemia diagnosis and genotype
	Diagnosis	SCD diagnosis and genotype
	Exposure	• HSCT date (as Day 0)
		Autologous HSCT with exa-cel infusion
		Allogeneic HSCT infusion
	Safety	Neutrophil recovery
	Outcomes	Platelet recovery
		• New malignancy, including hematologic
		New or worsening hematologic disorder
		• Mortality, cause
	Effectiveness	 Primary disease severity measures*
	Outcomes	Hemoglobin measures
		Iron concentration measures
		• Disease-related end-organ damage / dysfunction
		Iron overload management
	Additional Key	Demographics
	Variables	• Health status
		Mobilization and conditioning regimen
		Transplant-related complications
		Disease-related therapies
		Additional laboratory measures, including CBC
		• Pregnancy (with outcome)
	CBC: Complete B	lood Count; SCD: sickle cell disease; HSCT: hematopoietic
	stem cell trans	splantation
	*Includes red bloc	d cell transfusions (TDT and SCD), vaso-occlusive crisis
	episodes (SCI	D only).
Data Sources	Data from 2 existing	g international registries covering countries with expected access
	to exa-cel will be us	sed:
	EBMT Registry	y
	• CIBMTR Regi	stry
	Both the EBMT and	l CIBMTR Registries have primary data collection capabilities
	for supporting pharm	nacoepidemiologic research studies. Primary and secondary data
	collected via these 2	2 registries will allow for the characterization of longitudinal
	patterns in a broad i	ange of safety and effectiveness outcomes within cohorts of
	exa-cel treated patie	ents and allo-HSCT comparator patients in EU, UK, and US.
	Existing registry rep	porting forms and customized study-specific reporting forms
	jointly developed by	y the sponsor and registry operators will allow data to be
	collected on outcom	hes and other key variables essential to meet the objectives of this
	study. Data will be	collected at standard timepoints following receipt of therapy for
	the first post-transp	lant year (100 days, 6 months, and 1 year), and annually
	thereafter. The data	collection responsibilities of the participating transplant centers,
	including the efforts	s to ensure long-term patient follow-up as well as SAE reporting
	responsibilities, wil	l be outlined in the site agreements, as applicable.
Study Size	Exa-cel enrollment	targets include a minimum of 100 treated patients with TDT and
·	100 treated patients	with SCD for a minimum of 200 exa-cel treated patients across
	all regions. It is exp	ected that the enrollment period will be approximately 3 years,

though may be extended to up to 5 years enrollment. It is anticipated that there will be an approximately equal number of allo-HSCT comparator patients enrolled.

Data Analysis To meet the study objectives, data will be analyzed separately for each registry and each cohort at pre-specified timepoints over the study duration (see Milestones Section). In addition to the separate analyses within each registry, pooled analyses of key safety outcomes are planned at pre-specified timepoints (after 5-, 10-, and 15-year duration of follow-up is accrued for all enrolled patients). The results of the interim and final analyses will be presented in interim and final study reports.

Descriptive statistics will be presented for all study endpoints. Continuous variables will be summarized using the following descriptive summary statistics where appropriate: the number of observations, mean, standard deviation, 95% CI, median, minimum value, maximum value, and 25th and 75th percentile values. Categorical variables will be summarized using counts, percentages, and 95% CIs as appropriate. Cumulative incidence curves will be provided for select outcomes.

Within the TDT and SCD Exa-cel Cohorts, comparisons of the post-transplant period to pre-transplant period will be performed, as appropriate.

Between cohort results (TDT Exa-cel versus TDT Allo-HSCT; SCD Exa-cel versus SCD Allo-HSCT) will also be evaluated within each registry separately.

Subgroup analyses will be performed by age group, genotype, and/or other patient characteristics, as appropriate. Subgroup analyses by country of transplant may be performed if sufficient patient counts are available to preserve patient anonymity. Additional ad hoc statistical analyses may be implemented, as applicable (e.g., modeling to adjust for differences in cohort characteristics in between-cohort analyses, time-to-event analyses for select outcomes). The details of the analyses will be included in the statistical analysis plan.

Findings from the analyses of TDT and SCD Exa-cel Cohorts will also be contextualized using published literature on the progression of TDT and SCD under the standard of care.

Milestones	Milestone	Planned Date
	Start of data collection	2024
	End of data collection	2042
	Progress Report	31 August 2024
	Progress Report	31 August 2025
	Progress Report	31 August 2026
	Interim Analysis 1	31 December 2027
	Progress Report	31 December 2028
	Progress Report	31 December 2029
	Interim Analysis 2	31 December 2033
	Interim Analysis 3	31 December 2038
	Final report of study results	31 December 2043

5

AMENDMENTS AND UPDATES

None applicable.

6 MILESTONES

Study milestones are included in Table 1.

Table 1	Study Milestones
---------	------------------

Milestone	Data Included	Planned Date
Start of data collection	NA	2024
End of data collection	NA	2042
Registration in the HMA- EMA Catalogue	NA	Following Protocol Approval
Progress Report	NA	31 August 2024
Progress Report	Tentatively through 31 August 2024	31 August 2025
Progress Report	Tentatively through 31 August 2025	31 August 2026
Interim Analysis 1	Tentatively through 31 December 2026	31 December 2027
	(anticipated end of enrollment period)	
Progress Report	Tentatively through 31 December 2027	31 December 2028
Progress Report	Tentatively through 31 December 2028	31 December 2029
Interim Analysis 2	Tentatively through 31 December 2032	31 December 2033
	(all enrolled patients anticipated to reach 5 years of follow-up)	
Interim Analysis 3	Tentatively through 31 December 2037	31 December 2038
	(all enrolled patients anticipated to reach 10 years of follow-up)	
Final Report	Tentatively through 31 December 2042	31 December 2043
	(all enrolled patients anticipated to reach 15 years of follow-up)	

HMA-EMA Catalogue: Heads of Medicines Agencies and European Medicines Agency joint catalogue (former EU PAS Register); NA: not applicable

Milestones depicted in Figure 1 assume a 3-year enrollment duration with a study closure after the final enrolled patient has been followed for 15 years (i.e., Year 18). Study milestones and analysis dates (Table 1, Figure 1) are estimated and may shift due to final approval dates, enrollment needs and/or data availability.

Figure 1 Planned Data Collection Milestones

FU: follow-up; IA: interim analysis

Note: Timelines may shift slightly if enrollment is extended to 5 years duration.

7 RATIONALE AND BACKGROUND

7.1 Background

 β -thalassemia is an inherited autosomal recessive blood disease characterized by reduced hemoglobin (Hb) production. Caused by mutations in the *HBB* gene, disease severity varies across a spectrum from intermedia to thalassemia major. β -thalassemia major, also called transfusion-dependent β -thalassemia (TDT), is fatal within the first few years after diagnosis if left untreated. Symptoms of TDT appear within the first 2 years of life and include severe anemia, splenomegaly, bone marrow expansion, failure to thrive and ultimately, death.

Sickle cell disease (SCD) is caused by a single nucleotide substitution in which a valine replaces a glutamic acid at position 6 of the β -globin chain leading to an abnormal or sickle cell Hb (HbS). HbS polymerizes in the deoxygenated state producing abnormal, sickle shaped red blood cells (RBCs) with limited flexibility and lifespan. These rigid cells are responsible for painful vaso-occlusive crisis (VOC), chronic anemia, inflammation, stroke, organ failure, and early mortality.

Exagamglogene autotemcel (exa-cel) is a cellular product consisting of autologous CD34⁺ human hematopoietic stem and progenitor cells modified by CRISPR-Cas9-mediated gene editing of the erythroid enhancer region of the *BCL11A* gene located on chromosome 2. *BCL11A* is a transcriptional silencer of γ -globin gene expression and hence a negative modulator of fetal Hb (HbF) production. Shortly before birth, *BCL11A* is turned on and there is a switch from HbF to adult Hb (HbA), which is made up of 2 α -globin chains and 2 β -globin chains. The switch from HbF to HbA is mediated by a transcriptional switch from γ -globin to β -globin expression within the β -globin gene cluster located on chromosome 11. CRISPR-Cas9 is "clustered regularly interspaced short palindromic repeats and CRISPR-associated 9 nuclease". Cas9 is an enzyme that uses CRISPR guide RNA (gRNA) sequences to cleave a specific genomic locus that is complementary to the CRISPR gRNA. The goal of this genetic modification is to reactivate the expression of γ -globin messenger RNA in erythroid precursors, which in turn leads to an increase in HbF protein levels in adult erythroid cells.

Exa-cel is intended to treat disorders caused by genetic defects that affect the production or function of Hb molecules (β -thalassemia, SCD).

Information regarding long-term safety and effectiveness of therapy under the real-world conditions of use will be informative to patients, caregivers, and prescribers. Existing hematopoietic stem cell transplantation (HSCT) registries provide a mechanism to obtain these data.

7.2 Rationale

This 15-year observational, post-authorization, registry-based study will evaluate the long-term safety and effectiveness outcomes among patients with TDT and SCD who are treated with exa-cel in a real-world setting. This study will augment the exa-cel clinical program by enrolling and following both exa-cel-treated real-world patients as well as comparator patients receiving allogeneic HSCT (allo-HSCT) to treat TDT and SCD. While exact study cohort sizes are dependent upon commercial uptake and patient consent, it is expected that this study will enable data collection from a larger, more diverse sample of patients than included in the clinical trials. Collaboration with the European Society for Blood and Marrow Transplantation (EBMT) and Center for International Blood and Marrow Transplant Research (CIBMTR) patient registries allows access to the existing HSCT reporting platforms and minimization of excess reporting burden on the participating transplant centers.

8 RESEARCH QUESTIONS AND OBJECTIVES

8.1 Objectives

Primary

- 1. Evaluate long-term safety outcomes in patients who received exa-cel for treatment of TDT or SCD
- 2. Evaluate long-term safety outcomes in patients who received exa-cel for treatment of TDT or SCD in comparison to patients receiving allo-HSCT

Secondary

- 1. Evaluate long-term effectiveness outcomes in patients who received exa-cel for treatment of TDT or SCD
- 2. Evaluate long-term effectiveness outcomes in patients who received exa-cel for treatment of TDT or SCD in comparison to patients receiving allo-HSCT

8.2 Prior Hypotheses

This study will further characterize the effects of exa-cel treatment with real-world use, provide long-term follow-up of patients receiving treatment and provide descriptive analyses on specified safety and effectiveness outcomes using observational data. Because these analyses will be used

for active surveillance / hypothesis generation, no prior hypotheses are proposed. Though this is a hypothesis generating study, it is expected that the study results demonstrate that the safety profile of exa-cel in patients treated under real-world conditions is consistent with the clinical studies and that long-term treatment outcomes are not inferior to allo-HSCT outcomes.

9 **RESEARCH METHODS**

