9.5 Study Size

Exa-cel is an advanced therapeutic medicinal product targeted for individuals with 1 or more severe manifestations of rare hematologic disorders. HSCT for SCD and TDT is a rare procedure, with allogeneic transplants for SCD and TDT representing only a small fraction of the total annual HSCT volume managed by transplant centers. In 2019, hemoglobinopathies were only 1.4% of the HSCT volume reported to the EBMT¹⁵, and 1.1% of the reported volume in the US.^{16, 17} The average number of transplants performed historically (2016 through 2019) in Germany, France, Italy, UK, and US for patients with SCD and TDT who are 12 years of age and older without a matched donor (equivalent to the population indicated for exa-cel) is approximately 70 patients per year (CIBMTR data on file, EBMT data on file).¹⁶ It is expected that exa-cel will be available to only small numbers of patients in routine clinical practice.

As such, exa-cel enrollment targets include a minimum of 100 treated patients with TDT and 100 treated patients with SCD for a minimum of 200 exa-cel treated patients across all regions included in the study. It is expected that the enrollment period will be up to approximately 3 years, though may be extended to up to 5 years enrollment if the minimum sample size is not reached within 3 years.

It is anticipated that there will be an approximately equal number of allo-HSCT comparator patients enrolled. While eligibility for the Allo-HSCT Cohorts will be limited to patients aged 12 years and older, it will not be limited by donor type and may include patients from the larger pool of individuals receiving matched, mismatched or haploidentical donor transplants (see Section 9.1.2 for full inclusion / exclusion criteria).

Exa-cel uptake under real-world conditions is ultimately unknown and may be impacted by factors such as access and reimbursement, transplant center capacity to treat patients with newly available gene therapies, advances in allogeneic transplantation such as haploidentical transplant, potential availability of other gene or oral therapy products, and other unforeseen factors. Nevertheless, it is anticipated that approximately 1/3 of the final enrolled sample will be from European centers.

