9.7 Data Analysis

All analyses for this study will be performed by the respective statistical / programming teams using SAS, SPSS, R, or equivalent statistical software. All outcome variables specified in Sections 9.3.3 through 9.3.5 will be evaluated for both the exa-cel and allogeneic HSCT cohorts, including the TDT Exa-cel, TDT Allo-HSCT, SCD Exa-cel and SCD Allo-HSCT Cohorts. Patient-level data (pseudonymized) will additionally be available, for both exa-cel and allo-HSCT cohort participants, with patient consent / assent.

To meet the study objectives, data will be analyzed separately for each registry and each cohort at pre-specified timepoints over the study duration. Each interim report will include separate analyses of the data collected by each registry and will provide a descriptive comparison of the EBMT and CIBMTR patient populations in terms of (i) demographic and clinical characteristics, (ii) treatment(s) received, and (iii) outcomes. In addition to the separate analyses within each registry, pooled analyses of key safety outcomes (Section 9.3.3) will be performed at prespecified timepoints (after a 5-, 10-, and 15-year duration of follow-up is accrued for all enrolled patients), unless substantial heterogeneity is observed between the two registries. Any potential issues precluding variable harmonization across the two registries will be discussed in the analysis reports. Pooled analysis of additional outcomes may be performed if feasible and warranted. The results of the interim and final analyses will be presented in interim and final study reports.

Descriptive statistics will be presented for all study outcomes:

- **Continuous variables** will be summarized using the following descriptive summary statistics, where appropriate: the number of observations, mean, standard deviation, 95% CI, median, minimum value, maximum value, and 25th and 75th percentile values.
- **Categorical variables** will be summarized using counts, percentages, and 95% CIs, as appropriate.

Crude risks, crude relative risks with 95% CI, and odds ratios with 95% CI will be calculated for outcomes, as appropriate. Cumulative incidence, treating death as a competing risk, will be calculated and presented for select safety outcomes. Overall survival curves will be produced.

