9.7.3 Safety Analyses

Safety outcomes will be evaluated for each cohort from each registry at each time point of the post-transplant period. In addition to the separate analyses within each registry, pooled analyses of the safety outcomes listed below will be performed at pre-specified timepoints (after a 5-, 10-, and 15-year duration of follow-up is accrued for all enrolled patients), unless substantial heterogeneity is observed between the two registries. Any potential issues precluding variable harmonization across the two registries will be discussed in the analysis reports. Analyses will be performed overall and in subgroups by patient age group, genotype, country, and/or other category, as appropriate and if sufficient data are available. Additional analyses may be performed for outcomes deserving further investigation if sufficient data are available. Statistical testing may be performed comparing the frequencies or rates of outcomes from the TDT Exa-cel and TDT Allo-HSCT Cohorts, and the SCD Exa-cel and SCD Allo-HSCT Cohorts, if sufficient data are available.

• Neutrophil Recovery

Proportion of patients reaching the neutrophil recovery threshold, with the corresponding 95% CI, will be calculated at each timepoint of the post-transplant period until all patients have reached neutrophil recovery.

Time to neutrophil recovery, in days, will be calculated for each patient from Day 0, as reported by the registries.

The proportion of patients who recovered neutrophils by specific timepoints of interest (for example, by Day 42) will also be calculated.

Cumulative incidence curves detailing time to neutrophil recovery may be produced.

• Platelet Recovery

Platelet recovery threshold will vary for SCD and TDT cohorts.

Proportion (with 95% CI) of patients reaching the platelet recovery threshold will be calculated at each timepoint of the post-transplant period until all patients have reached platelet recovery.

Time to platelet recovery, in days, will be calculated for each patient from Day 0, as reported by the registries.

Cumulative incidence curves detailing time to platelet recovery may be produced.

• New Malignancy

Proportion (with 95% CI) of patients diagnosed with a new hematologic malignancy will be calculated for each timepoint of the post-treatment period.

Proportion (with 95% CI) of patients diagnosed with a new solid malignancy will be calculated for each follow-up of the post-treatment period.

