9.9.3 Sample Size Limitations

Small sample sizes are a known challenge inherent in working with rare disease populations.³³ Exa-cel therapy, indicated for individuals with the most severe phenotypes within known rare disease populations, is expected to only be available to relatively small numbers of individuals. Smaller sample sizes may limit identification of uncommon safety signals or prevent powerful analytic comparisons. In addition, given the smaller sample size, some subgroup analyses may not produce informative results. To maximize the data collection and inferential ability within this study, a broad range of hard endpoints (i.e., disease diagnoses) and early indicator (i.e., laboratory value) variables are included in this study; these variables, in combination with data on disease-related symptoms and therapies, will aid in characterizing the safety and durability of exa-cel effects. Moreover, data collection will occur at least annually, allowing repeated measures of patient outcomes over time.

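### Section 8.2 proposes no hypotheses, yet expects the results to demonstrate non-inferiority to allo-HSCT, which the described comparisons cannot show

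*Protocol*

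**What the plan says.** Section 8.2 describes the analyses as descriptive and meant for surveillance and hypothesis generation, and states that "no prior hypotheses are proposed". It goes straight on: "it is expected that the study results demonstrate that the safety profile of exa-cel" under real-world use matches the clinical studies, and that "long-term treatment outcomes are not inferior to allo-HSCT outcomes".

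Comparison with allo-HSCT is primary objective 2 for safety and secondary objective 2 for effectiveness (section 8.1). Three places describe how the cohorts will be compared:

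- Section 9.7: "Crude risks, crude relative risks with 95% CI, and odds ratios with 95% CI will be calculated for outcomes, as appropriate". Cumulative incidence for select safety outcomes and overall survival curves are also planned.
- Section 9.7.3: "Statistical testing may be performed comparing the frequencies or rates of outcomes from the TDT Exa-cel and TDT Allo-HSCT Cohorts", likewise for SCD, provided there are sufficient data. Section 9.7.4 repeats this for effectiveness.
- Section 9.7: between-cohort results are evaluated within each registry. Key safety outcomes are also pooled at 5, 10 and 15 years unless the registries differ substantially.

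Section 9.5 sets the exa-cel target at "a minimum of 100 treated patients with TDT and 100 treated patients with SCD for a minimum of 200 exa-cel treated patients". It anticipates roughly as many allo-HSCT patients and about one third of the sample from European centers. Section 9.9.3 concedes: "Smaller sample sizes may limit identification of uncommon safety signals or prevent powerful analytic comparisons".

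**The concern.** Demonstrating that one treatment is not inferior to another is a confirmatory conclusion. It needs a named outcome, a scale, a margin, and a confidence limit compared with that margin. A study that proposes no hypotheses has nothing of this kind to demonstrate.

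The consequence falls on how primary objective 2 is read. A comparison of frequencies or rates with no margin is most naturally a test of no difference. In small cohorts such a test often returns a non-significant result even when a real difference exists. Placed next to a protocol sentence that already expects a finding of not inferior, that result invites the reader to treat lack of evidence as confirmation. The fewer the patients and events, the more easily the expectation appears to be met.

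The other half of the sentence, demonstrating consistency with the clinical studies, has the same defect: it expects a confirmatory result without saying what would count as one.

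**Working it through.** **The text.** The two statements in 8.2 cannot both stand, and a statistical analysis plan could not reconcile them. If that plan sets a non-inferiority margin, the statement that no hypotheses are proposed is wrong. If it sets none, the expectation of demonstrating non-inferiority has no basis. Section 8.2 needs changing either way.

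**Inputs for the illustration.** The protocol gives no power-based sample size to reproduce: 100 + 100 = 200 is an enrollment target, and the text states no alpha, power, event risk or margin.

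- Cohort size: 100 per disease (the 9.5 minimum), with about 100 comparators.
- By registry: 100 × 1/3 ≈ 33 (EBMT) and 100 × 2/3 ≈ 67 (CIBMTR). This assumes that the one-third European share applies in each disease and each cohort.
- Event risks: assumed, 5% v 10% and 10% v 20%.
- Test: two-sided 5%. The protocol names no test, so Pearson chi-square and Fisher's exact test are both shown.

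**Chance of a non-significant result when the risk truly doubles.** For independent binomial counts a (exa-cel) and b (allo-HSCT), the probability of each pair, Bin(a; n, p_exa) × Bin(b; n, p_allo), is summed over all pairs that are not significant.

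| n per cohort | 5% v 10%: Pearson | 5% v 10%: Fisher | 10% v 20%: Pearson | 10% v 20%: Fisher |
|---|---|---|---|---|
| 100 | 73% | 81% | 48% | 56% |
| 67 | 80% | 89% | 64% | 71% |
| 33 | 88% | 97% | 79% | 88% |

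**One result at 100 v 100.** With 10 v 5 events, Fisher p = 0.28. The Newcombe 95% CI for the risk difference (exa-cel minus allo-HSCT) runs from -2.6 to +13.0 percentage points. The data show no significant difference, yet they do not exclude an excess of up to 13 points.

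**Precision.** The Wald half-width for a risk difference is 1.96 × √(2p(1−p)/n). At p = 10%:

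- n = 100: 1.96 × √(0.18/100) = 8.3 points
- n = 67: 10.2 points
- n = 33: 14.5 points

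**Why the margin matters.** With equal true risks and a one-sided 2.5% level, non-inferiority power is Φ(margin/SE − 1.96), where SE = √(2p(1−p)/n). For an assumed 10-point margin at n = 100:

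- p = 5%: SE = 0.0308, power Φ(3.24 − 1.96) = 90%
- p = 10%: SE = 0.0424, power Φ(2.36 − 1.96) = 65%
- p = 20%: SE = 0.0566, power Φ(1.77 − 1.96) = 42%

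At n = 33 the same margin gives 46%, 27% and 17%. Whether these cohorts could support a non-inferiority conclusion depends on the outcome and margin, and 8.2 names neither.

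**The case against.** The case on the other side has several sound parts.

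- The sentence is an expectation, introduced by a reminder that the study is hypothesis generating. It is not an objective or a decision rule. A reader might infer that the protocol commits the sponsor to a non-inferiority claim, or that the report will present a null test as one. The documents say neither.
- A reader might also infer that a test of difference is prescribed. No test and no null hypothesis is named; testing is optional and depends on sufficient data, which works against testing at 33 v 33.
- Confidence intervals are already planned, and the unfavourable limit of a relative risk shows the largest relative disadvantage not excluded. Section 9.9.3 discloses the small samples, and pooling of key safety outcomes brings the size back to about 100.
- The absence of a margin is not in itself a fault. The analysis plan and the content of Annex 6 are not shown, and either may say more.
- The 8.2 sentence ties the safety profile to the clinical studies and long-term treatment outcomes to allo-HSCT. Applying the non-inferiority wording to mortality or malignancy is a possible reading, not the only one.
- The event risks are assumed, and 100 per disease is a minimum. A general statement that a doubling of risk would usually be missed goes too far: for 10% v 20% at 100 v 100, Pearson misses it 48% of the time.

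These points limit the size of the concern but do not remove the contradiction. Calling the sentence an expectation does not make it descriptive, and a confidence interval supports non-inferiority only against a margin fixed in advance.

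**Conclusion.** The concern holds as a contradiction within section 8.2 that bears on how primary objective 2 may be interpreted. A study declared descriptive, with no hypotheses proposed, should not expect to demonstrate non-inferiority or consistency. The comparisons described in 9.7, 9.7.3 and 9.7.4 could not support either conclusion without a prior criterion.

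The possible size of the misreading is substantial but only illustrative. At the minimum cohort size, a true doubling of risk is non-significant in 48% to 81% of studies across the two assumed risk pairs and two tests. At 33 v 33 the range is 79% to 97%. These figures rest on assumed event risks, equal cohort sizes and a one-third European share in every cohort.

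A reader might infer that the comparison is invalid or that the study cannot meet its objectives. The documents do not support that: estimation with confidence intervals remains sound for a descriptive aim. The correction concerns wording and reporting only.

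**What to change.** 1. In section 8.2, replace the whole sentence that states the expectation, including the part about consistency with the clinical studies. Suggested text: *The study will describe the safety profile of exa-cel under real-world conditions and estimate differences from allo-HSCT with 95% CIs; no non-inferiority or equivalence conclusion will be drawn.*

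2. In sections 9.7.3 and 9.7.4, add that for mortality, new malignancy and the main effectiveness proportions the exa-cel minus allo-HSCT difference will be reported with its 95% CI alongside the planned relative risks and odds ratios. It should be adjusted or stratified for the confounders in section 9.9.2 where counts allow. Add also that a non-significant test will not be interpreted as similarity or non-inferiority.

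3. If the sponsor prefers to keep a non-inferiority claim, the outcome, time point, scale and margin must be fixed before any between-cohort outcome data are seen, that is before Interim Analysis 1 (report planned for 31 December 2027). Waiting until Interim Analysis 2 would allow the margin to be chosen with comparative results in hand. The statement that no prior hypotheses are proposed must then be removed.

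The cost is a few sentences and an extra column in the planned tables, with no new patients or data items. The sponsor gives up an informal statement of non-inferiority, and the reported intervals will look wide.
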